#### **11.6.4 Electrocardiograms (Ivacaftor Arm Only)**

Standard 12-lead ECGs will be performed using a machine with printout. Additional standard 12-lead ECGs will be performed at any other time if clinically indicated. The performance of all ECGs will adhere to the following guidelines:

- The subject will rest in the supine position for at least 5 minutes, if possible, before having an ECG performed.
- The ECG will be performed predose through the Week 24 Visit before any other procedures that may affect heart rate, such as blood draws. Following the Week 24 Visit, ECGs may be taken pre- or post-dose.

The ECG traces will be manually read at the study site at the Screening Visit and Safety Follow-up Visit. A printout of the ECG traces will be made for safety review by the investigator and maintained with source documentation. Clinically significant ECG abnormalities occurring during the study through the Safety Follow-up Visit will be recorded as AEs.

Study sites should use QTcF unless they receive approval in advance from the Vertex medical monitor or authorized designee to use QTcB.

To ensure safety of the subjects, a qualified individual at the study site will make comparisons to baseline measurements. If the QTcF is increased by >60 msec from the baseline or an absolute QTcF value is  $\geq 500$  msec for any scheduled ECG, 2 additional ECGs will be performed approximately 2 to 4 minutes apart to confirm the original measurement. If either of the QTcF values from these repeated ECGs remains above the threshold value (>60 msec from baseline or  $\geq 500$  msec), a single ECG will be repeated at least hourly until QTcF values from 2 successive ECGs fall below the threshold value that triggered the repeat measurement. A subject with a QTcF value above the threshold value will discontinue dosing.

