For the Ivacaftor Arm, the TE period will include the time period starting from the first dose date of the study drug in the current study to the Safety Follow-up Visit, or the last dose date + 28 days for subjects who do not have a Safety Follow-up Visit. The TE period will be used for safety analyses unless specified otherwise.

Unscheduled visits: Unscheduled visit measurements will be included in analysis as follows:

- In scheduled visit windows per specified visit windowing rules
- In the derivation of baseline/last on-treatment measurements.
- In the derivation of maximum/minimum on-treatment values and maximum/minimum change from baseline values for safety analyses.
- In individual subject data listings as appropriate.

Visit windowing rules: The analysis visit windows for protocol-defined visits in the Ivacaftor Arm are provided in Appendix B. The windows will be applied using the following rules for both scheduled and unscheduled visits. If no measurement is available within a visit window, the assessment will be considered missing for the visit. If there is more than one measurement available within the same visit window, the following rules will be used:

- For all safety parameters, if there are multiple measurements within a visit window, then 1) the record closest to the target day will be used, with the exception of the threshold analysis in which the worst record will be used; 2) if there are multiple records within the same distance of the target day, the latest record will be used; or 3) the Safety Follow-Up (SFU) visit will not be windowed; instead, the nominal visit will be used in relevant analyses.
- For all efficacy parameters, if there are multiple measurements within a visit window, the record at the scheduled visit will be used. Otherwise,
 - If there are no measurements at the scheduled visit, then the record closest to the target day will be used;

- If there are multiple records with the same distance to the target day, the latest record will be used.
- Assessments at the early treatment termination (ETT) visit will follow the windowing rules for regular visits, with the exception of the ETT visit occurs 21 days or later after the last dose, which will be treated as SFU visit.

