8.4.3 Electrocardiogram

For treatment-emergent ECG measurements, a summary of raw values and change from baseline values will be provided by visit for the following standard 12-lead ECG measurements: RR (ms), HR (bpm), PR (ms), QRS duration (ms), QRS axis (degrees), QT (ms), and QT corrected for HR intervals [QTcF (ms)].

The number and percentage of subjects meeting at least 1 threshold analysis criterion during the TE period for the Treatment Period will be summarized. The threshold analysis criteria are provided in Appendix E.

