	Week 96	672	[589, max(686, Date of Week 96 + 14)]

^a Visit name is used to report data in tables, listings and figures.

^b Target day time point per protocol is predose, except for ECG measurements.

^c Per section 8.1, it will remain as the SFU if it goes beyond the upper boundary of the window for the last scheduled visit.

Notes:

The analysis visit windows will be applied using the following rules for both scheduled and unscheduled visits:

1. If no numerical measurement is available within a visit window, the measurement will be considered missing for the visit.
2. If there is more than 1 numerical measurement available within the same visit window, use the following rules:
 - a. For efficacy parameters: if there are multiple measurements within a visit window, the measurement at the scheduled visit will be used. Otherwise,
 - i. If there are no measurements at the scheduled visit, then the measurement closest to the target day will be used; or
 - ii. If there are multiple measurements with the same distance to the target day, the latest measurement will be used.
 - b. For safety parameters: if there are multiple measurements within a visit window,
 - i. The measurement closest to the target day will be used; or
 - ii. If there are multiple measurements within the same distance from the target day, the latest measurement will be used.
 - iii. For tables of the extreme lab measurement based on ULN or LLN, convert the lab measurements into times of ULN or LLN first, and then select the extreme measurement

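### By-visit safety summaries use the latest same-day record, so a completed QTcF alert series contributes a sub-trigger repeat instead of the scheduled alert reading

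*SAP*

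**What the plan says.** SAP 8.1 lets unscheduled measurements into the analysis: "In scheduled visit windows per specified visit windowing rules". For safety parameters with several records in a window, the one closest to the target day is used, and on a tie "if there are multiple records within the same distance of the target day, the latest record will be used". Rule 2b in the notes to Appendix B repeats this: "If there are multiple measurements within the same distance from the target day, the latest measurement will be used". The safety sentence in 8.1 carries one exception: "with the exception of the threshold analysis in which the worst record will be used". The same section also feeds unscheduled values into on-treatment maximum/minimum values and maximum/minimum changes for safety analyses.

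Efficacy is treated differently: "For all efficacy parameters, if there are multiple measurements within a visit window, the record at the scheduled visit will be used". Closeness and lateness decide only when there is no scheduled record.

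Protocol 11.6.4 sets the QTcF alert at a rise of more than 60 msec from baseline, or a value of 500 msec or more, on any scheduled ECG. Two further ECGs follow, 2 to 4 minutes apart. If either is still above the threshold, "a single ECG will be repeated at least hourly until QTcF values from 2 successive ECGs fall below the threshold value" that triggered the repeat. SAP 8.4.3 then plans that "a summary of raw values and change from baseline values will be provided by visit" for QTcF and the other ECG intervals.

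**The concern.** The two rules interact. The protocol produces extra ECGs because a reading was high and stops when later readings are lower. The SAP then selects the last of them for the by-visit table. Which record is analysed therefore depends on the result, and for QTcF the pull is always downward.

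The distance rule can do something similar to laboratory and vital-sign data. A retest prompted by an abnormal value can land nearer the target day than the scheduled measurement and replace it.

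Adverse events, laboratory values, ECGs and vital signs, and ophthalmologic examinations make up the primary endpoint. The by-visit tables are where a reader looks for drift over 96 weeks and for the largest change at a given visit. Those means and maxima should not depend on whether a high reading happened to prompt a repeat.

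**Working it through.** The plan gives no figure to reproduce, so the check is of the rules themselves, followed by sizing under stated assumptions.

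**1. Do same-day records tie?** Appendix B windows and target days are in study days. All readings of a same-day series have the same distance to the target day, so the latest wins.

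**2. Where does a completed alert series end?** There are two paths:
- both confirmatory ECGs are below the trigger, and the last is below;
- at least one is not, and ECGs continue until two in a row are below, so the last is below.

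Either way the latest record is below the trigger.

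**3. Worked case (illustrative values).** Week 24, Day 168, baseline taken as 445 msec so that only the 500 msec limit is in play (505 − 445 = 60, not more than 60). The readings are 505, 502, 498, 490 and 470 msec. The distance is |168 − 168| = 0 for all five.
- By-visit value: 470 msec.
- Threshold-analysis value: 505 msec.
- Scheduled value: 505 msec.

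**4. Simulation of the alert procedure.** None of these inputs is in the documents. With baseline 400 msec, reading SD 15 msec, and 100,000 visits at each true visit mean:

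| True visit mean (msec) | Alert visits | Latest record below trigger | Mean of first minus latest (msec) |
|---|---|---|---|
| 430 | 2,255 | 2,255 | 36.1 |
| 450 | 25,287 | 25,287 | 25.2 |
| 470 | 74,680 | 74,680 | 25.4 |

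With reading SD 10 to 20 msec and a true increase of 40 to 50 msec, the gap between the alert reading and the retained reading runs from about 18 to 36 msec.

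**5. Effect on the visit mean.** The shift per alert is gap / n. With n = 75 (the planned enrolment, SAP 6.2):
- 18 / 75 = 0.24 msec
- 36 / 75 = 0.48 msec

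The shift scales with the number of alerts. Three alerts with an assumed gap of 60 msec would give 3 × 60 / 75 = 2.4 msec. With fewer subjects at a visit, each alert weighs more. The visit maximum can fall by the whole gap, as in step 3 (505 − 470 = 35 msec).

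**6. The distance route.** Protocol 11.6.2 asks for confirmatory liver tests within 48 to 72 hours, so take a retest d = 2 or 3 days after a visit at offset o from the target day. It replaces the scheduled value when |o + d| ≤ |o|, since a tie goes to the later record. With o from −7 to +7 (15 whole days, the ±7-day visit window):
- d = 2: o = −7 to −1, so 7 of 15 (47%).
- d = 3: o = −7 to −2, so 6 of 15 (40%).

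This assumes visit days spread evenly over the window. If the visit is on or after the target day, the scheduled value stays.

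**The case against.** **The alert value survives elsewhere.** A reader might infer that the alert is dropped from the safety analysis, or that parameters outside the liver and QTcF threshold tables have no safeguard. The documents support neither reading. The worst-record exception stands in the same SAP sentence as the tie rule. Maximum/minimum derivations take in unscheduled values for safety parameters generally. Appendix B rule 2b selects the extreme for laboratory tables based on normal limits. SAP 8.4.2 lists out-of-range laboratory values from scheduled and unscheduled visits, and SAP 8.4 lists all safety data. Clinically significant abnormalities become adverse events. Protocol 12.3.4.3 plans counts by maximum QTcF and maximum increase. This objection stands and confines the point to by-visit summaries. One qualification is that SAP 8.4.2 to 8.4.4 do not name a maximum/minimum table for every parameter. The visible part of Table 11-7 has only absolute QTcF bands, but the table may be cut short in the extracted text, so no omission is claimed.

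**The 18 to 36 msec gap is not an error in the child's value.** It is first reading minus last, and most of it is regression to the mean. In the simulation with SD 15 msec:
- a true rise of 50 gives a mean alert reading of 69.1 (19.1 too high) and a mean retained reading of 43.5 (6.5 too low);
- a true rise of 40 gives 67.0 (27.0 too high) and 37.2 (2.8 too low).

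For an alerting child the retained value is on average nearer the truth. This also stands. It does not rescue the group summary: chance high readings are replaced while chance low readings are kept, so the visit mean is pulled below its true value.

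**The retained value need not be normal.** It is only below the trigger, and 499 msec would qualify.

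**The rule may work differently in practice.** The SAP does not say that repeats are stored as separate timed records, or that the latest is decided by clock time. That is a real condition on the finding, and also a reason to write the rule down.

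**Nothing is tested.** All safety analysis is descriptive and the study is not powered. That limits the consequence, but descriptive tables are the study's main output.

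**Conclusion.** The concern holds for by-visit safety summaries and no further. If repeat ECGs are stored as separate timed records, every completed QTcF alert series puts a sub-trigger repeat into the by-visit raw and change summaries in place of the scheduled alert reading. The selection depends on the result and biases those means and maxima downward.

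The size is minor to moderate. Under the assumed variability (reading SD 10 to 20 msec, true increase 40 to 50 msec), each alert lowers the visit mean by about 0.2 to 0.5 msec at n = 75, and the by-visit maximum may miss the alert value. The documents give no alert frequency, so a total effect cannot be stated. The laboratory and vital-sign route is partial. For a retest 2 to 3 days later it applies to 6 or 7 of 15 visit offsets if visit days are uniform over ±7 days, and only to early visits.

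**What to change.** In SAP 8.1 and Appendix B rule 2b, state that by-visit safety summaries use the scheduled-visit record, as efficacy summaries already do. For a same-day series, state that this means the first, scheduled reading. Allow unscheduled repeats into by-visit summaries only when no valid scheduled value exists. Leave the worst-record rule for threshold analyses and the maximum/minimum derivations as they are.

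The cost is two sentences and one programming rule. The downside is small: a scheduled value judged to be a sample or device error must be flagged invalid explicitly, because its repeat would no longer overwrite it.

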**Table 3-1 Schedule of Assessments for VX15-770-126 (Ivacaftor Arm: Same-day Transition Subjects From Study 124 Part B)**

Event/Assessment	Day 1 c	Treatment Period (Day 1 Through Week 96)		ETT Visit a	Safety Follow-up Visit b	24-Week Follow- up OE
		Weeks 12, 36, 60, and 84 (± 7 Days)	Weeks 24, 48, 72, and 96 (± 7 Days)	As Soon as Possible After the Last Dose	4 Weeks (± 7 Days) After the Last Dose	24 Weeks (+ 14 Days) After the Last Dose
Informed consent	X					
Confirm eligibility	X					
Clinic visit	X	X	X	X	X	
Study drug dose determination d	X	X	X			
Length and weight e	X	X	X	X	X	
Physical examination f	X	X	X	X	X	
Vital signs g	X	X	X	X	X	
12-lead ECGs g, h	X		X	X	X	
Serum chemistry and hematology	X	X	X	X	X	
Ophthalmologic examination i	X		X	X j		X

a The ETT Visit is to be scheduled as soon as possible after the last dose of ivacaftor. If the ETT Visit occurs 3 weeks or later after the last dose of ivacaftor, the Safety Follow-up Visit will not be required. Subjects who elect to receive commercially available ivacaftor will be discontinued from ivacaftor dosing and will complete the ETT Visit and Follow-up OE.

b For subjects who elect to receive commercially available ivacaftor, the Safety Follow-up Visit will not be required.

c The Day 1 Visit will be the same day as the Week 24 Visit of Study 124 Part B. Any Study 126 Day 1 assessments performed at the Week 24 Visit of Study 124 Part B do not need to be repeated. Day 1 results should be taken from the Week 24 Visit in Study 124 (if applicable) on which these data are available (including demographics and medical history), except for the signing of informed consent, confirmation of eligibility, and IVRS/IWRS contact.

d The ivacaftor dose for each subject will be reassessed based on body weight and adjusted if necessary (see Section 9.4).

e Length and weight measurements will be performed predose through the Week 24 Visit (see Section 11.5.1).

f Full physical examinations will be performed at the ETT and Safety Follow-up Visits; abbreviated physical examinations will be performed at all other study visits.

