- Assessments at the SFU visit will follow the windowing rules for regular visits if they fall within the upper boundary of the window for the last scheduled visit; it will remain as the SFU if it goes beyond the upper boundary of the window for the last scheduled visit.

Visit windowing rules will not be used for the Observational Arm as they will not add value.

Incomplete/missing data will not be imputed, unless specified otherwise.

Outliers: No formal statistical analyses will be performed to detect or remedy the presence of statistical outliers, unless specified otherwise.

Multiplicity: No multiplicity adjustment will be performed for hypothesis testing.

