	Week 72	504	[463, 546]
	Week 84	588	[547, 630]
	Week 96	672	[631, max(686, Date of Week 96 + 14)]
	Safety Follow-up Visit	NA	Use nominal visit
Standard 12-Lead ECG	Baseline	Not applicable	parent study baseline
	Week 24	168	[2, 252]
	Week 48	336	[253, 420]
	Week 72	504	[421, 588]
	Week 96	672	[589, max(686, Date of Week 96 + 14)]
	Safety Follow-up Visit	NA	Use nominal visit
Ophthalmologic Exam	Baseline	Not applicable	parent study baseline
	Week 24	168	[2, 252]
	Week 48	336	[253, 420]
	Week 72	504	[421, 588]
	Week 96	672	[589, max(686, Date of Week 96 + 14)]
	24-Week Follow-up OE	NA	Use nominal visit
Efficacy Assessments			
Weight Length Weight-for-length BMI Weight-for-age z-score Length-for-age z-score Weight-for-length z-score BMI-for-age z score	Baseline	Not applicable	parent study baseline
	Week 12	84	[2, 126]
	Week 24	168	[127, 210]
	Week 36	252	[211, 294]
	Week 48	336	[295, 378]
	Week 60	420	[379, 462]
	Week 72	504	[463, 546]
	Week 84	588	[547, 630]
	Week 96	672	[631, max(686, Date of Week 96 + 14)]
	Safety Follow-up Visit	NA	Use nominal visit ^c

Fecal elastase-1 Fecal calprotectin Sweat chloride Qualitative Microbiology Multiple Breath Washout	Baseline	Not applicable	parent study baseline
	Week 24	168	[2, 252]
	Week 48	336	[253, 420]
	Week 72	504	[421, 588]
	Week 96	672	[589, max(686, Date of Week 96 + 14)]

^a Visit name is used to report data in tables, listings and figures.

^b Target day time point per protocol is predose, except for ECG measurements.

^c Per section 8.1, it will remain as the SFU if it goes beyond the upper boundary of the window for the last scheduled visit.

Table 11-5 Analysis Visit Windows for Safety and Efficacy Assessments – IVA-naïve subjects (Subjects Not From Study 124 Part B or Part A/B)

Assessment	Visit ^a	Target Study Day ^b	Analysis Visit Window (in study days)
Safety Assessments			
Serum Chemistry	Baseline	1	≤1
	Week 2	14	[2, 35]
	Week 8	56	[36, 70]
	Week 12	84	[71, 105]
	Week 18	126	[106, 147]
	Week 24	168	[148, 210]
	Week 36	252	[211, 294]
	Week 48	336	[295, 378]
	Week 60	420	[379, 462]
	Week 72	504	[463, 546]
	Week 84	588	[547, 630]
	Week 96	672	[631, max(686, Date of Week 96 + 14)]
Safety Follow-up Visit	NA	Use nominal visit	
Hematology	Baseline	1	≤1
	Week 4	28	[2, 42]
	Week 8	56	[43, 70]
	Week 12	84	[71, 105]
	Week 18	126	[106, 147]
	Week 24	168	[148, 210]
	Week 36	252	[211, 294]
	Week 48	336	[295, 378]
	Week 60	420	[379, 462]
	Week 72	504	[463, 546]
	Week 84	588	[547, 630]

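### The SAP's rules for Safety Follow-up data conflict, and one of them lets growth values taken 21 to 35 days off drug be reported at treatment visits

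*SAP*

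**What the plan says.** **Timing.** Protocol Table 3-1 schedules the SFU visit "4 Weeks (± 7 Days) After the Last Dose", that is, 21 to 35 days off drug. Weight, length, vital signs, ECG, chemistry and hematology are taken then. Sweat chloride, fecal samples, microbiology, multiple breath washout (MBW) and the ophthalmologic examination (OE) are not.

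**Who has one.** Under Protocol 9.1.1.5, early discontinuers complete an ETT visit and an SFU visit. The SFU is waived if the ETT falls 3 weeks or later after the last dose, or if the subject moves to commercial ivacaftor.

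**SAP 8.1, safety parameters.** "the Safety Follow-Up (SFU) visit will not be windowed; instead, the nominal visit will be used in relevant analyses".

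**SAP 8.1, ETT bullet.** ETT assessments follow the regular windows, except that an ETT 21 or more days after the last dose counts as SFU: "the ETT visit occurs 21 days or later after the last dose, which will be treated as SFU visit".

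**SAP 8.1, next bullet.** "Assessments at the SFU visit will follow the windowing rules for regular visits if they fall within the upper boundary of the window". The window meant is that of the last scheduled visit, and past its boundary the data stay labelled SFU. The bullet names no parameter type, and the last scheduled visit is not defined.

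**SAP Appendix B, Tables 11-4 and 11-5.** Every safety SFU row reads "Use nominal visit" with no footnote. The growth SFU row has the same entry plus footnote c: "Per section 8.1, it will remain as the SFU if it goes beyond the upper boundary of the window for the last scheduled visit". The Week 96 window for labs, vital signs and growth is "631, max(686, Date of Week 96 + 14" (brackets omitted), with target Day 672.

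**Choosing among several records in a window.** For safety, "the record closest to the target day will be used, with the exception of the threshold analysis in which the worst record will be used". For efficacy, the scheduled-visit record comes first, then the record closest to target. Neither rule requires the subject to be on drug.

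**The concern.** For safety parameters the two SFU statements in Section 8.1 cannot both govern. One never windows the visit; the other windows it whenever it falls early enough. Two programmers working from the same SAP could produce different by-visit tables.

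The second statement also works against the ETT bullet just before it. That bullet takes late ETT visits out of the regular windows by calling them SFU; the SFU bullet then sends SFU visits back in. ETT visits occur only in early discontinuers, so if the boundary is Week 96 the exception has almost no effect.

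For growth, Section 8.1 and footnote c point the same way, and what they prescribe is the problem: a weight or length measured 3 to 5 weeks after stopping can be tabulated as a treatment-visit value, in early stoppers only. The same subject then drops out of the SFU row.

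The treatment-emergent period does not screen these values out, because it runs to the SFU visit.

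**Working it through.** The plan gives no figure of its own here, so the check is day arithmetic on the Appendix B windows.

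**Inputs from the documents.** SFU lag 28 ± 7 = 21 to 35 days. 12-weekly windows (rollover labs, vital signs, growth): [2,126], [127,210], [211,294], [295,378], [379,462], [463,546], [547,630], then Week 96 from 631 to at least 672 + 14 = 686. Targets are 84, 168, ..., 588, 672, and each window before Week 96 ends 42 days after its target.

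**Assumptions.** Last dose L equally likely on Days 85 to 630 (630 − 85 + 1 = 546 days); scheduled visits on target; ETT at L + 3; SFU at L + 21, L + 28 or L + 35.

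**1. Completers with on-time visits.** Week 96 falls on Days 665 to 679 and the last dose is that morning. SFU is at least 21 days later, so it never falls within Week 96 + 14. It reaches Day 686 or earlier in one of 15 × 15 = 225 day combinations: Week 96 on Day 665, SFU on Day 686. There the Week 96 record is 7 days from target and the SFU record 14, so the Week 96 record is kept. Completers are essentially untouched.

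**2. Early discontinuers, boundary read as Week 96.** The latest SFU is Day 630 + 35 = 665, below 686. All 546 days fall inside a regular window at every lag: 100%.

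**3. Early discontinuers, boundary read as the subject's own last visit.** The SFU is inside if L + lag ≤ target + 42. That allows 43 − lag last-dose days for each of 7 windows, less one because Day 84 is outside the range:
- lag 21: 22 × 7 − 1 = 153; 153/546 = 28%
- lag 28: 15 × 7 − 1 = 104; 104/546 = 19%
- lag 35: 8 × 7 − 1 = 55; 55/546 = 10%

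On this reading the SFU shares its window with a scheduled visit. A visit up to 7 days before target puts the SFU at least 21 − 7 = 14 days after target, so the scheduled record wins unless it is missing.

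**4. SFU as the only record in its window (Week 96 reading).** This happens when a window starts after the ETT day and on or before the SFU day, which gives lag − 3 last-dose days for each of the 7 window starts (127 to 631):
- lag 21: 18 × 7 = 126; 126/546 = 23%
- lag 28: 25 × 7 = 175; 175/546 = 32%
- lag 35: 32 × 7 = 224; 224/546 = 41%

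Example: last dose Day 280, ETT Day 283 (Week 36 window), SFU Day 308 (Week 48 window). The Week 48 weight is then a value 28 days off drug.

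Sensitivity to ETT timing: with ETT at +1 day the multiplier is lag − 1, giving 26%/35%/44%; with ETT at +14 it is lag − 14, giving 9%/18%/27%. Spreading last dose over Days 2 to 664 and the lag over 21 to 35 days, with ETT at +1 to +14, gives 15 to 29% for these windows and 22 to 43% for the denser growth and vital-sign windows of IVA-naïve subjects.

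**5. SFU as the selected safety record (Week 96 reading, bullet taken literally).** Adding the cases where the SFU is at least as close to target as the other records gives 327, 352 and 383 of 546 days: 60%/64%/70%. Example: last dose Day 300, ETT Day 303 (33 days from target 336), SFU Day 328 (8 days from target). The SFU value becomes Week 48.

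**The case against.** The best defence is that the SAP already settles the safety parameters. The specific safety rule and every safety SFU row in both Appendix B tables send SFU data to the nominal visit, and footnote c is attached only to growth. Against that stands one general bullet. It follows directly on the efficacy sub-rules and may have been meant as one of them, although its wording does not say so. This largely stands: a careful programmer would probably keep safety SFU data at the nominal visit.

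It follows that the 60 to 70% in step 5 is a safety figure on the less likely reading. It does not transfer to growth, where the scheduled-visit record comes first. The 100% in step 2 likewise depends on taking the boundary as Week 96.

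It is also fair that SFU data belong in treatment-emergent summaries by design, since that period runs to the SFU visit. Only the visit label is in question. The growth endpoints are tertiary and descriptive, and keeping late growth values may have been deliberate.

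None of this removes the growth effect. Footnote c confirms the conditional rule there, no text defines its boundary, and no on-drug condition limits it. The wording conflict for safety also remains until the bullet is restricted.

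**Conclusion.** The SFU rules are inconsistent and need one correction. The effect the documents support is on weight, length and the measures derived from them: values 21 to 35 days off drug can be reported at treatment visits. Effects on by-visit labs, ECGs and vital signs are possible only if the unrestricted bullet is applied over the safety rule.

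The illustrative size is 100% of SFU visits inside a treatment window on the Week 96 reading, or 28%/19%/10% on the own-last-visit reading. The SFU is the sole record in 23%/32%/41% on the Week 96 reading. These rest on uniform last-dose days, on-target visits and ETT at +3 days. The number of early discontinuers is not given, so the effect on any table mean cannot be sized.

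A reader might infer three stronger things that the documents do not support:
- That safety tables will certainly carry off-drug values. Appendix B assigns every safety SFU row to the nominal visit.
- That every early discontinuer is affected. Those who switch to commercial ivacaftor need no SFU; only those with an SFU or an ETT 21 or more days after the last dose can be affected.
- That the main results are touched. Sweat chloride, fecal markers, microbiology, MBW and OE are not scheduled at the SFU visit. Treatment-emergent adverse event counts and the LFT and QTcF threshold tables use the whole treatment-emergent period, whatever the visit label.

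**What to change.** Delete the SFU bullet in SAP 8.1 and footnote c in Tables 11-4 and 11-5. State one rule for safety and efficacy alike: SFU assessments, and ETT visits 21 or more days after the last dose, are summarised at the nominal SFU visit and never enter a treatment-visit window.

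At minimum, state that the SFU bullet does not apply to safety parameters, and define the last scheduled visit as either Week 96 or the subject's own last visit. This removes the ambiguity but still allows off-drug growth values at treatment visits.

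The cost is one SAP edit before database lock; SAP Section 3 has later changes documented in the clinical study report. The downside is that a few by-visit growth cells lose an off-drug value, which would still appear in the SFU row and the listings.
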